## 5.4 Inclusion/Exclusion Criteria

**Table 1. Inclusion/Exclusion Criteria**

Inclusion Criteria	Exclusion Criteria

• Diagnosis of TBI or Ischemic Stroke

• 2-10 years post neurologic event having completed rehabilitation

• Age 18 - 80 years old

• Medically stable

• Fluent in English

• Moderately impaired cognitive function as defined by AMPS Processing sub-scale measures falling below 1.0 logits

• Moderately impaired cognitive capacity as

	

• Have BOTH TBI and Ischemic Stroke

• Intracranial lesions or hemorrhagic stroke

• Other primary neurologic diagnosis

• Any dementia diagnosis

• History of/or symptoms of psychotic spectrum disorders (i.e., bipolar, schizophrenia)

• Persons with alcohol use disorder (AUD) and/or substance use disorder (SUD) diagnoses confirmed by clinical and/or scientific experts

• Reside in an extended care facility

• Less than 2 years post TBI or ischemic stroke

• Anti-epileptic medications for seizure activity

defined by having two or more scores falling $\geq 1$ standard deviation below age normed expectations on: the RBANS index scores, DKEFS Color-Word Trials 3 and 4 scale scores, and/or WAIS-IV Digit Span scaled score	
 
Seizure within the past 3 months or active seizure
 
Contraindications to MRI/iTBS such as ferromagnetic or other magnetic sensitive metals implanted in their head or with in 30cm of the treatment coil or implanted devices in or near the head
 
Medication changes within 3 months of starting participation
 
Currently receiving therapy services
 
Pregnancy
 
FIM scores for problem solving <3 or >4 OR memory <4 or >5, or changes in FIM scores during screening process
 
Neurostimulants that cannot be safely withdrawn
 
Bilateral ischemic stroke
 
Mild or severe impairments in cognitive capacity or cognitive function
 
CHF, implanted pacemakers or defibrillators, or cochlear implants
 
Heart valve with metallic materials
 
Questionable test validity as indicated by DOT (E-score <math>\geq 17</math>) or BRIEF (Negativity <math>\geq 6</math>; Infrequency <math>\geq 3</math>; Inconsistency <math>\geq 8</math>)
 
RBANS Total Scale < 70
 

---	---

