***Telephone Screening-Part 2: Self-Report of Cognitive Impairment:***

Part-2 involves a second broad screening of cognitive function based on the Functional Independence Measure (FIM) completed by telephone interview. This incremental cognitive screening approach will circumvent potential diluting effects of including Veterans at extremes of the functional impairment continuum (mild, severe). For the 6-months prior to screening, Veterans requiring minimal or moderate assistance on problem-solving (scores: 3 or 4) and/or minimal assistance or supervision on memory (scores: 4 or 5), will remain eligible. These cut-off points are based on recent research by the study team^6 indicating that Veterans with these scores for these items most likely have short-term memory issues, impeding function, but not long-term memory issues. Veterans and/or healthcare surrogates will be asked to report location of any non-VA emergency room (ER), intensive and post-acute care treatment and for consent to collect these medical records for further screening.

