The Repeatable Battery for the Assessment of Neuropsychological Status (RBANS) will be used to broadly assess a range of cognitive domains (e.g., Learning/Immediate Memory, Language, Attention) whereas the Wechsler Adult Intelligence Scale (WAIS-IV) Digit Span subtest will be used to measure working memory. The Delis-Kaplan Executive Functioning System (DKEFS) Color-Word Interference subtest will be used to measure processing speed and executive function whereas the Behavior Rating Inventory of Executive Function (BRIEF) will be used to measure the Veteran's perception of executive function across nine domains as well as overall executive functioning, behavioral regulation, and metacognition. We will also examine testing validity in terms of inadequate effort using the Dot Counting Test and response validity using the BRIEF.

We define moderately impaired cognitive capacity as having two or more scores falling  $\geq 1$  standard deviation below age normed expectations on: the RBANS index scores, DKEFS Color-Word Trials 3 and 4 scale scores, and/or WAIS-IV Digit Span scaled score. Any Veteran with a RBANS Total Scale  $< 70$  will be excluded as this cut-off point suggests likely presence of severe cognitive impairment or major neurocognitive disorder. Any Veteran with DOT (E-score:  $\geq 17$ ) or BRIEF-A scores (Negativity  $\geq 6$ ; Infrequency  $\geq 3$ ; Inconsistency  $\geq 8$ ) indicative of questionable testing validity will be excluded. The use of these test performance criteria will identify Veterans who are not employable and are struggling with day to day life requiring assistance with complex Independent Activities of Daily Living due to cognitive impairments.

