For Veterans remaining eligible, we seek to link cognitive capacity with cognitive function in daily life as measured with the Assessment of Motor and Process Skills (AMPS) Processing sub-scale, which is a reliable and valid measure of cognitive function defined according to the quality of performance of daily tasks dependent on cognitive abilities (Independent Activities of Daily Living or IADL). The AMPS IADL tasks are selected according to patient profiles and the value placed on the task by the patient, which is determined through a structured interview. We will utilize the streamlined AMPS (AMPS), which will examine the quality of performance of 1

unique IADL while adhering to all administration and scoring procedures. Scoring on the AMPS is not continuous, rather scores may indicate varying levels of impairment depending on the skill of the task examined. All raw AMPS scores are, using AMPS dedicated analytic software, transformed to interval level measures (on a logit scale) and calibrated to neutralize any potential bias due to rater severity or leniency. These calibrations define the boundaries of the five categories of difficulty. We define moderately impaired cognitive function as AMPS Processing sub-scale measures falling below 1.0 logits. This cut-off indicates the Veteran cannot live independently as they have difficulty performing cognitive-based tasks/ADL effectively.

This AMPS sub-scale includes IADL items calibrated by difficulty and grouped by five categories (Easiest, Much Easier than Average, Easier than Average, Average and Hardest). The easiest items fall within the 'Uses' domain, which includes tasks requiring use of tools and materials relative to intended uses (e.g., pencil sharpener for pencils but not crayons). The hardest items fall within the 'Accommodates' domain where preventing ineffective task performance requires accommodation (e.g., ironing multiple garments, putting garments away). Across the average difficulty category, there are 45 IADL within five cognitive domains (terminates, navigates, handles, adjusts, continues). The 'terminates' domain, for example, involves appropriate task cessation (e.g., no premature cessation, no persistence) whereas the 'continues' domain involves continuing a task without pauses or delays until task completion.

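### Moderate cognitive function has an upper AMPS limit but no lower one, so the exclusion for severe function has no AMPS rule behind it

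*Combined protocol and SAP*

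**What the plan says.** Inclusion (section 5.4, Table 1): cognitive function must be moderately impaired, "as defined by AMPS Processing sub-scale measures falling below 1.0 logits". The optional-study table has the same criterion. Section 5.5 restates it as the study's definition: "We define moderately impaired cognitive function as AMPS Processing sub-scale measures falling below 1.0 logits". The only meaning given to the threshold is "This cut-off indicates the Veteran cannot live independently".

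Exclusion (both tables): "Mild or severe impairments in cognitive capacity or cognitive function". No AMPS value is given for severe.

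Intent: the telephone-screening text in section 5.1 says the stepwise approach is meant to "circumvent potential diluting effects of including Veterans at extremes of the functional impairment continuum (mild, severe". The Abstract, the Introduction and the Study Design section all describe a cohort with a homogeneous, moderate level of impairment.

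Other measures do have a lower limit. Section 5.5 excludes an RBANS Total Scale below 70, "as this cut-off point suggests likely presence of severe cognitive impairment or major neurocognitive disorder". FIM problem solving must be 3 or 4 and FIM memory 4 or 5, and Table 1 excludes scores outside those bands.

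**The concern.** Mild, moderate and severe are used as mutually exclusive labels, and both ends are supposed to be screened out. For function measured by AMPS, only the mild end has a number. The stated range for moderate runs downward without limit, so it contains every score that anyone might call severe. The inclusion definition and the severe-function exclusion in the same table therefore do not fit together.

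Two things depend on this. First, a sample that is homogeneous in level of impairment is the reason given for pooling stroke and TBI. Second, AMPS is an Aim 1 outcome and belongs to both the immediate-effects and the persisting-effects measures, so an open lower tail widens the baseline spread of an outcome. If severe function is judged without a written rule, the severity admitted could also differ between stroke and TBI. Table 3 (potential covariates) does not list entry AMPS, so the plan has no stated adjustment for it.

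**Working it through.** **1. Limits by instrument, as printed.** The plan states no figure that could be reproduced here, so the main check sets the rules side by side.

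| Measure | Where | Mild side excluded | Severe side excluded |
|---|---|---|---|
| FIM problem solving | 5.1, Table 1 | above 4 | below 3 |
| FIM memory | 5.1, Table 1 | above 5 | below 4 |
| Capacity (RBANS, DKEFS, WAIS-IV) | 5.5, Table 1 | fewer than two scores at least 1 SD below norm | RBANS Total below 70 |
| Function (AMPS Processing) | 5.5, Table 1 | 1.0 logits or above | none stated |

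AMPS is the only row without a severe-side value.

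**2. Could section 5.5 supply one indirectly?** The meaning given to 1.0 logits is a single threshold for independent living. It separates mild from the rest, not moderate from severe. The five AMPS categories do not help: "These calibrations define the boundaries of the five categories of difficulty". They grade tasks by difficulty and are not bands of impairment in the person.

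**3. Do the other limits bound AMPS?** The Introduction describes FIM as a broad link, then refined by neuropsychological tests and by observed IADL performance. FIM is obtained by telephone interview. Section 5.1 makes in-person testing, including AMPS, the confirmation of moderate capacity and function. A Veteran with FIM in range, RBANS Total of 70 or more and a very low AMPS score passes every numerical limit in the table above.

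**4. Illustrative size (assumptions, not document figures).** Let screened AMPS be normal with mean μ from 0.3 to 0.7 and SD σ from 0.5 to 0.8 logits, cut above at 1.0. With b = (1 − μ)/σ and λ = φ(b)/Φ(b):

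- entry SD = σ√(1 − bλ − λ²)
- share of those admitted who lie below f = Φ((f − μ)/σ)/Φ(b)

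At μ = 0.3, σ = 0.8: b = 0.875 and λ = 0.2721/0.8092 = 0.336. Entry SD = 0.8√(1 − 0.294 − 0.113) = 0.616. Share below 0 = 0.3538/0.8092 = 43.7%. Share below −0.5 = 0.1587/0.8092 = 19.6%.

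At μ = 0.7, σ = 0.5: b = 0.6 and λ = 0.3332/0.7257 = 0.459. Entry SD = 0.5√(1 − 0.275 − 0.211) = 0.358. Share below 0 = 0.0808/0.7257 = 11.1%. Share below −0.5 = 0.0082/0.7257 = 1.1%.

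Across the grid:

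| Lower limit (example only) | Entry SD | Share of those admitted who lie below it |
|---|---|---|
| none (as written) | 0.36 to 0.62 | not applicable |
| −0.5 | 0.34 to 0.41 | 1% to 20% |
| 0 | 0.27 to 0.28 | 11% to 44% |

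The example limits show sensitivity only and are not proposals. The grid ignores the earlier FIM and RBANS selection, which would pull these figures down if those measures track AMPS.

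**5. When would this distort Aim 1?** Suppose the treatment effect on gain is α + βS for a Veteran with entry severity S. The apparent moderation by diagnosis is then β × (mean S in stroke − mean S in TBI). It is zero if either factor is zero. A severity difference between diagnoses is not enough. The treatment effect must also vary with severity.

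**The case against.** The strongest reply is that eligibility criteria apply jointly. A reader might infer that one Veteran can be both eligible and excluded. The documents do not support that: meeting one inclusion item does not confer eligibility, and a Veteran judged severe is excluded. What remains is that the exclusion gives staff no AMPS value to apply, and the printed definition labels every such score moderate.

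A reader might also infer that severely impaired Veterans will enter freely. That goes too far. The two-sided FIM screen is aimed at both extremes of function. RBANS Total below 70, any dementia diagnosis and residence in extended care are also excluded, and section 5.5 applies AMPS only to those still eligible. The tail reaching AMPS is already thinned. The residue is Veterans whose FIM and AMPS disagree, and the documents do not say how common they are.

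Figure 1 summarises exclusions by screening step and is not shown, so a lower AMPS limit printed only there cannot be ruled out. Table 1 and section 5.5 would still have to agree with it.

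A further tempting reading is that Aim 1 is biased. Treatment is randomised within diagnosis, so wider baseline spread alone creates no diagnosis-by-treatment interaction. Distortion needs both factors in step 5, and the documents establish neither. Nor do they describe case-by-case exclusion, which is only one way of applying an undefined term.

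Finally, the gap does not require the homogeneity claim to be abandoned, because the FIM link stays two-sided.

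**Conclusion.** The concern holds as a conflict between stated rules. In the readable text, moderate function on AMPS has no lower limit, and the exclusion of severe function in both eligibility tables has no AMPS value. Read literally, the exclusion is empty; read otherwise, it rests on unstated judgement. The other criteria reduce the practical effect but do not bound the instrument meant to confirm moderate function in person.

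The size cannot be established from the documents. The illustrative ranges rest entirely on the assumed normal distribution and grid, and the conflict does not depend on them. The consequence for Aim 1 is a possibility that the plan could guard against cheaply, not a demonstrated bias. The conclusion is subject to what Figure 1 shows.

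**What to change.** **Eligibility text.** Reconcile the AMPS definition with the severe-function exclusion in Table 1, the optional-study table, section 5.5 and Figure 1. There are two ways:

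- state the AMPS range the investigators intend, and tie the severe-function exclusion to it; or
- state that severity of function is bounded only by FIM, and limit the homogeneity claim for AMPS function accordingly.

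The choice and any value belong to the investigators; no cut-off is proposed here. The cost is wording, with perhaps slightly slower recruitment if a lower limit is set.

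**Analysis.** Add entry AMPS, already collected at in-person screening, as a baseline covariate in the Aim 1 AMPS model (section 5.6). As a sensitivity analysis, add an entry-AMPS-by-treatment term. The main effect alone would not separate moderation by severity from moderation by diagnosis; the interaction term addresses that. The cost is one or two degrees of freedom with 48 participants. This is not negligible: the immediate-effects AMPS is given to half of each diagnosis-by-arm cell on each treatment day, so 48/2/2/2 = 6 Veterans per cell per day. That is why the interaction term is suggested only as a sensitivity analysis.

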#### OPTIONAL STUDY INCLUSION/EXCLUSION CRITERIA

Inclusion Criteria	Exclusion Criteria

 
Diagnosis of TBI
 
2-10 years post neurologic event having completed rehabilitation
 
Age 18 - 80 years old
 
Medically stable
 
Fluent in English
 
Moderately impaired cognitive function as defined by AMPS Processing sub-scale measures falling below 1.0 logits
 
Moderately impaired cognitive capacity as defined by having two or more scores falling <math>\geq 1</math> standard deviation below age normed
 
	
 
Have BOTH TBI and Ischemic Stroke
 
Intracranial lesions or hemorrhagic stroke
 
Other primary neurologic diagnosis
 
Any dementia diagnosis
 
History of/or symptoms of psychotic spectrum disorders (i.e., bipolar, schizophrenia)
 
Persons with alcohol use disorder (AUD) and/or substance use disorder (SUD) diagnoses confirmed by clinical and/or scientific experts
 
Reside in an extended care facility
 
Less than 2 years post TBI or ischemic stroke
 
Anti-epileptic medications for seizure activity
 
Seizure within the past 3 months or active seizure
 

expectations on: the RBANS index scores, DKEFS Color-Word Trials 3 and 4 scale scores, and/or WAIS-IV Digit Span scaled score
	
 
• Contraindications to MRI/iTBS such as ferromagnetic or other magnetic sensitive metals implanted in their head or within 30cm of the treatment coil or implanted devices in or near the head
 
• Medication changes within 3 months of starting participation
 
• Currently receiving therapy services
 
• Pregnancy
 
• FIM scores for problem solving <3 or >4 OR memory <4 or >5, or changes in FIM scores during screening process
 
• Neurostimulants that cannot be safely withdrawn
 
• Bilateral ischemic stroke
 
• Mild or severe impairments in cognitive capacity or cognitive function
 
• CHF, implanted pacemakers or defibrillators, or cochlear implants
 
• Heart valve with metallic materials
 
• Questionable test validity as indicated by DOT (E-score <math>\geq 17</math>) or BRIEF (Negativity <math>\geq 6</math>; Infrequency <math>\geq 3</math>; Inconsistency <math>\geq 8</math>)
 
• RBANS Total Scale <math>< 70</math>
 

--	---

## 5.5 Study Evaluations

Data collected will include data related to safety in the administration of the experimental intervention, iTBS, immediate and persisting effects of the intervention, and acceptability of the intervention based on Veteran fatigue ratings, mood, agitation, and measures of Veteran-perceived suitability.

*Electronic Medical Records:* Screening procedures involving a review of the Veteran's medical records to screen for eligibility and safety to participate. A HIPAA waiver will be requested to provide the research clinician access to the Veteran's medical record to screen for study eligibility based on the approved inclusion/exclusion criteria. If a Veteran is receiving care outside the VA, a medical records request will be initiated to obtain necessary records to support inclusion/exclusion criteria screening. Medical records will also be screened for documentation by a physician that the Veteran lacks decision making capacity. If the Veteran continues to meet all inclusion/exclusion criteria after telephone screening and medical record review, the Veteran will be scheduled for in person eligibility screening and either the Veteran or healthcare surrogate with assent of the Veteran will provide informed consent.

*Self-report, Observational, Neuropsychological, Cognitive Capacity and Functional Outcomes, Effort Testing, and Structured Interview Data:* In person eligibility confirmation testing, study outcomes and covariate data will be collected for each Veteran during screening, at enrollment, and throughout their participation in the study.

The Repeatable Battery for the Assessment of Neuropsychological Status (RBANS) will be used to broadly assess a range of cognitive domains (e.g., Learning/Immediate Memory, Language, Attention) whereas the Wechsler Adult Intelligence Scale (WAIS-IV) Digit Span subtest will be used to measure working memory. The Delis-Kaplan Executive Functioning System (DKEFS) Color-Word Interference subtest will be used to measure processing speed and executive function whereas the Behavior Rating Inventory of Executive Function (BRIEF) will be used to measure the Veteran's perception of executive function across nine domains as well as overall executive functioning, behavioral regulation, and metacognition. We will also examine testing validity in terms of inadequate effort using the Dot Counting Test and response validity using the BRIEF.

We define moderately impaired cognitive capacity as having two or more scores falling  $\geq 1$  standard deviation below age normed expectations on: the RBANS index scores, DKEFS Color-Word Trials 3 and 4 scale scores, and/or WAIS-IV Digit Span scaled score. Any Veteran with a RBANS Total Scale  $< 70$  will be excluded as this cut-off point suggests likely presence of severe cognitive impairment or major neurocognitive disorder. Any Veteran with DOT (E-score:  $\geq 17$ ) or BRIEF-A scores (Negativity  $\geq 6$ ; Infrequency  $\geq 3$ ; Inconsistency  $\geq 8$ ) indicative of questionable testing validity will be excluded. The use of these test performance criteria will identify Veterans who are not employable and are struggling with day to day life requiring assistance with complex Independent Activities of Daily Living due to cognitive impairments.

For Veterans remaining eligible, we seek to link cognitive capacity with cognitive function in daily life as measured with the Assessment of Motor and Process Skills (AMPS) Processing sub-scale, which is a reliable and valid measure of cognitive function defined according to the quality of performance of daily tasks dependent on cognitive abilities (Independent Activities of Daily Living or IADL). The AMPS IADL tasks are selected according to patient profiles and the value placed on the task by the patient, which is determined through a structured interview. We will utilize the streamlined AMPS (AMPS), which will examine the quality of performance of 1

unique IADL while adhering to all administration and scoring procedures. Scoring on the AMPS is not continuous, rather scores may indicate varying levels of impairment depending on the skill of the task examined. All raw AMPS scores are, using AMPS dedicated analytic software, transformed to interval level measures (on a logit scale) and calibrated to neutralize any potential bias due to rater severity or leniency. These calibrations define the boundaries of the five categories of difficulty. We define moderately impaired cognitive function as AMPS Processing sub-scale measures falling below 1.0 logits. This cut-off indicates the Veteran cannot live independently as they have difficulty performing cognitive-based tasks/ADL effectively.

This AMPS sub-scale includes IADL items calibrated by difficulty and grouped by five categories (Easiest, Much Easier than Average, Easier than Average, Average and Hardest). The easiest items fall within the 'Uses' domain, which includes tasks requiring use of tools and materials relative to intended uses (e.g., pencil sharpener for pencils but not crayons). The hardest items fall within the 'Accommodates' domain where preventing ineffective task performance requires accommodation (e.g., ironing multiple garments, putting garments away). Across the average difficulty category, there are 45 IADL within five cognitive domains (terminates, navigates, handles, adjusts, continues). The 'terminates' domain, for example, involves appropriate task cessation (e.g., no premature cessation, no persistence) whereas the 'continues' domain involves continuing a task without pauses or delays until task completion.

Veterans who progress to enrollment will create a set of 11 IADL AMPS tasks according to meaningfulness, reported difficulty with performance and as indicated/agreed upon by the researcher according to whether they can be carried out in a clinic setting. To be valid, test items/IADL used in the assessment are not standardized across patients, rather they are selected on the basis of patient profiles and the value/importance placed on the task by the patient. The selected IADL are then setup to accommodate the different ways a person completes the task or equipment/item variations they may use. IADL tasks from this set of 11 tasks will be selected, without replacement, each time the AMPS is administered (Table 2) meaning that a unique task is used with each AMPS administration.

**Immediate Effects (ImE) Measures.** For TBI and stroke, *magnitude of cognitive gains immediately after a single session of iTBS to the DLPFC are unknown. For healthy controls, however, working memory shows the most consistent and largest effects (g=.938).* Thus, we will measure immediate change in cognitive capacity according to the domain of working memory using the **MDS**, which is based on the WAIS-IV Digit Span as it enables repeated administration and has an extensive research base and a structure that lends itself to adaptation with less theoretical likelihood of alternate form reliability issues. To minimize potential reliability issues, the *study Neuropsychologist created 6 alternate forms that each retain the underlying WAIS-IV Digit Span subtest structure as closely as possible. Each form uses identical instructions, number of practice and test items, and discontinuation and scoring criteria. Each form also includes a unique systematic randomization of digits where number strings follow the same internal structure including minimization of the digits '9' and '5' in a single string (i.e., 'phonetic similarity'), exclusion of repeated digits and '0' for forward/backward trials, consistent placement of repeated digits and '0's as they occur in the original sequencing trials, and introduction of the sequencing trials with a 'no manipulation' item. Further, no more than two sequential digits are used in any trial, and any instances of sequential digits in the original item content are reflected in the adapted trials.* As each alternate MDS form will be administered *three times in 30 min intervals*, we will **minimize practice effects** by doing an initial randomization of the ordering for administration of the alternate forms. Thus, each Veteran

across all interventions will be tested with the alternate forms in identical order. Since we are not actually testing and establishing the validity of each form, it is critical that the test conditions be identical across participants. If the alternate forms are not perfectly equivalent, then this identical order allows us to control for this issue across participants.

For measuring immediate changes in cognitive function, we will use the aforementioned **AMPS**. For each of the *three administrations, in 30-min intervals*, a unique task will be randomly selected (without replacement) from the set of tasks developed during Step 4 (Fig 1). Thus, the same IADL is never repeated for the same Veteran.

**Persisting Effects (PE) Measures.** This battery includes the same five tests/sub-tests administered during screening (Fig 1, Step-4: AMPS, RBANS, WAIS-IV Digit Span, DKEFS subtests and BRIEF-A). As the BRIEF-A will be re-administered, the study Neuropsychologist will review BRIEF-A scores and, if there are compelling reasons, Veterans with scores suggesting atypical validity will be withdrawn. This battery also includes tests to measure change in mood: Columbia Suicide Severity Rating Scale (C-SSRS) *Beck Anxiety Inventory (BAI)*, and the *Posttraumatic Stress Disorder Checklist (PCL)*. To assess fatigue, we will use the Fatigue Severity Scale (FSS), which is a self-report measure of prior-week fatigue during nine activities and current fatigue. To measure behavioral features of agitation, we will use the *Agitated Behavioral Scale (ABS)*.

Table 2: Instrumentation: Testing Battery					
Immediate Outcome Effects (ImE)	Hrs/Admin	Aims	Variable Types	# Reps	
AMPS	1.5	1 & 2	Continuous (logit)	3	
Modified Digit Span (MDS)	0.2	1 & 2	Proportional (% correct)	3	
Persisting Effects Testing Battery (PE)	Hrs/Admin	Aims	Variable Types	# Reps	
Repeatable Battery for Assessment of Neuropsych Status (RBANS)	1.0	2	Continuous (normed score)	5	
Weschler Adult Intelligence Scale (WAIS-IV) Digit Span			Proportional (% correct)	5	
Delis-Kaplan Executive Functioning System (DKEFS): Color-Word			Continuous (normed score)	5	
Behavior Rating Inventory of Executive Function (BRIEF)			Continuous (normed score)	5	
AMPS	1.5	2	Continuous (logit)	5	
PTSD Checklist (PCL)	0.1	2 & 3	Mean # symptoms/ severity	5	
Columbia Suicide Severity Rating Scale (C-SSRS)	0.1	2 & 3	Raw score (Veteran rating)	5	
Beck Anxiety Inventory (BAI)	0.1	2 & 3	Raw score (Veteran rating)	5	
Agitated Behavior Scale (ABS)	0.1	2 & 3	Raw score (research clinician rating)	5	
Fatigue Severity Scale (FSS): Prior Week Daily Living Score	0.1	2 & 3	Raw score (Veteran rating)	5	
Fatigue Severity Scale (FSS) L VASF Current Fatigue Rating	0.1	2 & 3	Raw score (Veteran rating)	5	

